### 5.4 Trial Design

This is a prospective, multi-centre, phase IV, biomarker-strategy design trial with a randomised control group in which adult liver transplant recipients will undergo IS withdrawal. Enrolled participants will be randomised 1:1 to either: 1) Non-Biomarker-based IS weaning (Weaning-All; Arm A); or 2) Biomarker-based IS weaning (Arm B). In participants allocated to Arm A IS will be withdrawn regardless of the result of the biomarker test. Among participants allocated to Arm B, only those found to be biomarker-positive (Arm B+, i.e. potentially tolerant) will be offered IS withdrawal, while biomarker-negative participants (Arm B-, i.e. potentially non-tolerant) will remain on their

baseline maintenance IS. This will allow us to demonstrate that the biomarker is a useful test to personalise IS by offering drug withdrawal only to those participants who are likely to complete the process successfully, avoiding unnecessary rejections among those who have not developed tolerance. Comparing the outcome of IS withdrawal between arms A and B+ will provide direct evidence of the clinical usefulness of the test as a function of its predictive accuracy. We have established that for the biomarker to drive safe IS withdrawal its Positive Predictive Value  $(PPV = \frac{Number Actually Tolerant}{Number Biomarker+})$  should be no less than 0.80, and its sensitivity at least 070. To account for centre effects, we will use stratified randomization. Furthermore, to avoid biases, participants undergoing drug withdrawal and their physicians will be blinded to the biomarker results. Participants randomized to Arm B- will know their biomarker status, and will be maintained in the study until they complete 48 months of follow-up post randomisation. They will contribute to secondary clinical outcomes and to the evaluation of the stability of the tolerance signature.

Cost and quality of life (HrQOL) assessments will be conducted alongside the trial to estimate the health-economic implications of the 2 different strategies. Furthermore, sequential biological specimens will be collected to conduct ancillary mechanistic studies. Recruitment will take place in 14 European liver transplant units (King's College Hospital, Royal Free London, Newcastle, Birmingham, Leeds, Edinburgh, Cambridge, Leuven, Hannover, Berlin, Barcelona, Dublin, Cliniques Universitaires Saint-Luc and Palermo-ISMETT).

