#### 8.2 Randomisation

Participants will be randomized 1:1 to either: 1) Non-Biomarker-based IS weaning (Arm A); or 2) Biomarker-based IS weaning (Arm B). In participants allocated to Arm A IS will be withdrawn regardless of the result of the biomarker test. Participants allocated to Arm B will be offered IS withdrawal only if they are classified as tolerant (Arm B+), while they will remain on maintenance IS if classified as non-tolerant (Arm B-).

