### 10.3.3 Randomisation Visit (4-6 weeks post liver biopsy)

Subjects identified as eligible for the clinical trial based on all screening procedures including liver biopsy results will attend a Randomisastion Visit that needs to occur within 6 weeks of performing the biopsy, and within 2 weeks of receiving the email from LIFT with the randomisation results In participants randomised to IS withdrawal the Randomisation Visit will mark the beginning of the IS withdrawal protocol.

- Review of inclusion / exclusion criteria
- Liver function tests (LFT)
- Blood draw for mechanistic studies
- Metabolic panel (HbA1c, fasting glucose, fasting total colesterol, LDL, HDL)
- HLA antibodies
- Treatment-related diseases history infection (CMV, fungal, other), biliary conditions, type II diabetes, kidney failure (possibly due to CNI), PTLD, cancer.
- Randomisation
- Adverse events
- Concomitant medications
- HrQOL assessment

Please note: Start decreasing the IS doses as per section 8.3 of this protocol.

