# 11. VISITS AND PROCEDURES SCHEDULE

#### 11.1 Table 2: Transplantation Centre Visits Schedule

Assessment / Visit	Baseline	Screening	М	М	М	М	М	М	М	М	М
	- 7 Wks	- 4 Wks	0	6	12	18	24	30	36	42	48
Informed consent	Х										
Demographics: gender, DOB, ethnicity	Х										
Height and weight	Х										
Medical history (pre & post transplantation)	Х										
Interval history 		Х	Х	Х	Х	Х	Х	Х	Х	Х	Х
Treatment-related diseases history			Х	Х	Х	Х	Х	Х	Х	Х	Х
Physical examination	Х	Х	Х	х	Х	Х	Х	Х	Х	Х	X
Vital signs	Х	Х	Х	х	Х	Х	Х	Х	Х	Х	X
Liver biopsy 		X 									X 
Diagnosis of biomarker test		Х									X
Biochemistry panel	Х	Х	Х	х	Х	Х	Х	Х	Х	Х	X
Hematology (FBC)	Х	Х	Х	х	Х	Х	Х	х	х	Х	Х
Liver function tests 	Х	Х	Х	х	Х	Х	Х	Х	Х	Х	X
Blood/ urine HCG test (females only)	Х										
HLA type of recipient and of donor (if available)	Х										
Autoantibody panel	Х										
IS drug 12-hour trough levels (as appropiate)	Х	Х	Х	Х	Х	Х	Х	Х	Х	Х	Х
Viral serology	Х										
MDRD eGRF	Х										
Inc. / Exc. Criteria	Х	Х	Х								
Metabolic panel			Х	х	Х	Х	Х	х	х	х	X
Blood draw for mechanistic studies 		Х	Х	х	Х	Х	Х	Х	Х	Х	X
Gut microbiome		Х				Х					X
Health Economics Questionnaire				х	Х	Х	Х	Х	Х	Х	X
EQ-5D Questionnaire			Х	х	Х	Х	Х	х	х	х	X
SF-36 and NIDDK Questionnaires			Х		Х		Х		Х		Х
Randomisation			Х								
Adverse Events 	Х	Х	Х	Х	Х	Х	Х	Х	Х	Х	Х
Concomitant Medication 	Х	X	Х	х	Х	Х	Х	х	х	Х	X
Fibroscan		Х			Х		х		Х		X

Information will also be collected during telephone visits (following each liver function test assessment).
 Protocol liver biopsies additional to screening one will be performed at 12 and 24 months post successful IS

weaning or at 48 months post randomization for patients on maitenance IS treatment.

Additional arm-specific schedule of liver function test monitoring is outlined in section 10.4.

Performed every three months for patients undergoing liver function test monitoring at the Transplant Centre.
 Wks weeks prior to randomization

M months from randomization

M0 randomisation visit

3

		~	Period														2			
Assessments	Volume (mL)	Screening	М 0	M 3	M 6	M 9		M 15	M 18		M 24			M 33	M 36			M 45	M 48	Rejection
Frozen PBMC (flow cytometry, epigenetic studies)	50	x	x		x		x		x		x				x				x	x
Whole blood Tempus tubes (gene expression profiling)	6	x	x		x		x		x		x		x		x		x		x	x
Serum (HLA alloantibodies)	5	x	x				x												x	x

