#### 12.2 Pharmaco-economic and quality of life assessments

Health related Quality of Life (HrQOL) Assessment: we will employ the Short-Form 36 Health Survey (SF-36) and/or the EQ-5D as generic surveys. SF-36 represents the most prominent generic measure in assessing patient's HrQOL following liver transplantation (27). In contrast, EQ-5D is the preferred generic measure for assessing QOL in adults, according to the Reference Case by NICE (28). By applying preference values from population studies to EQ-5D health states we will be able to generate utility values that will be used in quality-adjusted life years (QALY) and cost-per-QALY-analyses (28, 29). In addition, we will also assess QOL using disease-specific questionnaires (29, 30). The NIDDK Liver Transplant Database QOL questionnaire contains 63 items on 6 subscales that cover general health, role function, social function, psychological status, personal function, and measures of liver disease (27). Participants will be asked to complete the stated questionnaires on the following time points: inclusion, months 3, 6, 9, 12, 18, 24, 36, 48 (final study visit), and in case of rejection episodes. We expect differences in QOL to occur between arm A and B and between arm B+ and B-. Due to the higher risk of rejection, during the initial 6-9 months of the study QOL of B+ participants could be worse than those in arm B-. In the long run, they might be better off due to the fact that they are not dependent on IS and may have a reduction in IS side effects.

Assessment of Costs: costs will be assessed both from a healthcare and a societal perspective. For the healthcare perspective, only direct costs that accrue during the study period will be assessed (i.e. costs for IS medication, clinical visits, admissions, biomarker stratification). For the societal perspective, additional costs such as patient's absence from work, among others, will be accounted for. Resource utilization will be measured during the trial using a specific questionnaire, that will capture drug utilization, hospitalization, and diagnostic, therapeutic, and laboratory services consumed by patients. Resource utilization will be valued using prices relevant to the NHS. To calculate expected costs for the biomarker-guided weaning strategy, a micro-costing of the stratification process will be conducted.

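### The first quality-of-life questionnaires fall at a visit timed after the emailed randomisation result, and nothing requires them before the participant learns the allocation

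*Protocol*

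**What the plan says.** Section 10.3.3 (Randomisation Visit) sets the visit within 6 weeks of the biopsy and "within 2 weeks of receiving the email from LIFT with the randomisation results". Its list of procedures includes both randomisation and "HrQOL assessment". For participants allocated to withdrawal, weaning begins at this visit.

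The lists for the Baseline visit (Section 10.3.1) and the Screening Visit (Section 10.3.2) contain no quality-of-life item. In Table 2, the rows "EQ-5D Questionnaire" and "SF-36 and NIDDK Questionnaires" have their first mark at M0, with none at week -7 or week -4. Table 2 also marks randomisation at M0.

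Two other sections bear on the order. Section 8.2.1 has site staff enter the randomisation system only after consent, collection of all baseline data and confirmation of eligibility. It then has confirmation emails sent to key staff, some with the allocation and some without. Section 12.2 gives the questionnaire time points as "inclusion, months 3, 6, 9, 12, 18, 24, 36, 48 (final study visit), and in case of rejection episodes" and does not define inclusion.

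On blinding, Section 5.4 keeps weaned participants and their physicians unaware of the biomarker result, but not of the weaning itself. It adds: "Participants randomized to Arm B- will know their biomarker status". It does not say when they are told.

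**The concern.** A baseline value should be measured before allocation can influence it. Here the only scheduled baseline for quality of life sits at a visit that the protocol times from the randomisation result. A participant who has just learned that weaning will start, or that it will not, may answer questions on anxiety, mood and general health differently.

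The stake is specific. Section 9.2.1 defines the quality-of-life endpoint as change associated with withdrawal. Quality of life and health-economic impact are secondary objectives 2 and 3 in Section 5.3. Section 12.2 expects differences between A and B and between B+ and B-, and uses EQ-5D to derive QALYs. If the M0 score has already moved with the allocation, change from M0 absorbs part of that reaction. No later analysis can recover the missing pre-allocation value.

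**Working it through.** The protocol gives no figure to reproduce here, so the check is a comparison of sections, followed by the algebra of a shifted baseline.

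**Order of events, by section**

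| Source | What it implies for the first questionnaires |
|---|---|
| 10.3.1, 10.3.2 | None at Baseline or Screening |
| Table 2 | First at M0; randomisation also at M0 |
| 10.3.3, timing sentence | M0 follows the emailed result by up to 2 weeks, so the allocation already exists |
| 10.3.3, procedure list | Randomisation and the questionnaires are both done at M0; the bullets carry no order |
| 8.2.1 | All baseline data precede the randomisation request |
| 12.2 | At inclusion, undefined |

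The timing sentence in 10.3.3 and the procedure list beneath it cannot both describe the same step, unless randomisation in the list means telling the participant or acting on the result. Section 8.2.1 would settle the matter only if the M0 questionnaires counted as baseline data. They are not in the list that 10.3.1 labels as baseline assessments. A centre can therefore follow the text and collect the forms before or after disclosure.

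**Who knows what at M0.** A and B+ participants learn by M0 at the latest that they are being weaned, because weaning starts then. B- participants will know their biomarker status and that they stay on maintenance; the time is not stated.

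**Size of the affected group.** From Section 15, 148 are randomised 1:1 and about 50% are expected to be biomarker-positive:

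- Arm B: 148 × 0.5 = 74
- Arm B-: 74 × 0.5 = 37, which is half of Arm B

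**Bias from a shifted M0 score.** Let s_W be the mean shift in M0 score among weaned participants and s_N the mean shift in B-, with d = s_N − s_W. A shift s in the M0 score changes the group's mean change from M0 by −s. Let b be the slope of the outcome on baseline.

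- B+ minus B-, difference in change: −s_W + s_N = d. Baseline-adjusted: b × d.
- A minus B, difference in change: −s_W + (0.5 s_W + 0.5 s_N) = 0.5 d. Baseline-adjusted: 0.5 × b × d.
- A minus B+: −s_W + s_W = 0, because both groups are weaned and both are blinded to the biomarker result.

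**Illustration only.** The protocol gives neither d nor b. Assuming d = 2 SF-36 points and b between 0.5 and 0.7:

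| Contrast | Change score | Baseline-adjusted |
|---|---|---|
| B+ vs B- | 2 | 0.5 × 2 = 1.0 to 0.7 × 2 = 1.4 |
| A vs B | 0.5 × 2 = 1 | 0.5 × 1.0 = 0.5 to 0.5 × 1.4 = 0.7 |
| A vs B+ | 0 | 0 |

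The results scale linearly with d; at d = 0 there is no bias.

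**The case against.** The strongest reply is that Section 8.2.1 already requires baseline data before randomisation, so the M0 forms, read as baseline data, would come first. The emails are described as going to key staff, and an allocation held by staff is not one known to the patient. The participant may be told at M0 after completing the forms. This stands in part. A reader might infer that B- participants already know they have been classified as non-tolerant when they answer. The protocol does not say so, because Section 5.4 gives no time of disclosure. What remains is that nothing prevents disclosure first, and the sections disagree on the order.

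A reader might also infer that every quality-of-life comparison is affected. The stated blinding does not support that: A and B+ receive the same news, so only contrasts involving B- are exposed, and A versus B at about half strength.

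Recall periods soften the effect somewhat. Much of the SF-36 asks about the past 4 weeks and the NIDDK symptom section about the past month. With M0 at most 2 weeks after the email, at least half of such a window precedes the result. EQ-5D asks about today and has no such cushion, and a long recall window does not prevent current mood from colouring the answers.

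Finally, Section 16.2 treats secondary analyses as exploratory, and Sections 12.2 and 16.2 do not state a baseline-adjusted QALY analysis. That limits the consequence but does not remove it, because the endpoint is itself defined as change.

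**Conclusion.** The point holds as a scheduling defect. As written, the plan permits a quality-of-life baseline taken after allocation and after the participant knows it, and its sections contradict each other on the order. The possible bias lies in B+ versus B- (size d for change scores, b × d when baseline-adjusted) and, at about half that, in A versus B. A versus B+ has no evident differential shift.

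Neither the direction nor the size of d can be derived from the protocol; the 2-point example is an assumption. The dilution by half rests on the expected 50% biomarker-positive rate. The zero for A versus B+ rests on the blinding to the biomarker result being kept. The primary endpoint and the sample size are untouched. Only the secondary quality-of-life results, and any QALY analysis that adjusts for baseline utility, are at risk. The correction is worth making because the loss cannot be repaired in analysis and the remedy is cheap.

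**What to change.** Reconcile Sections 8.2.1, 10.3.3 and 12.2 and Table 2 so that they give one order of events. State whether the randomisation request is made before or at M0, define inclusion in Section 12.2, and say when B- participants are told their status.

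Require the first SF-36, NIDDK and EQ-5D to be completed after eligibility is confirmed and before the randomisation request. If that is not workable, require at minimum that they be completed before the participant is told the allocation, and record the completion date and time.

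The cost is a small scheduling burden. Table 2 has no visit between Screening and M0, so under the preferred option the forms would be completed remotely or the request made at M0 once they are done. The minimum option needs no extra visit. Moving the forms to week -7 or -4 would also protect the baseline, but it is a trade-off. Screening failures, who are not randomised (Section 6.3), would also complete three questionnaires, including the 63-item NIDDK form. Utility would also be measured 4 to 7 weeks before weaning starts.

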#### 10.3.3 Withdrawal visit from study

- Adverse events
- Concomitant medications
- Confirm the participant's agreement for the data and samples collected up to this point to be used for analysis.

### 10.4 Monitoring of Liver Function Tests

Participants undergoing IS withdrawal will have liver function tests performed every 3 weeks during the weaning period and the 6 months after complete IS withdrawal, monthly during the following 6 months, every 2 months during the following 6 months, and every 3 months thereafter. Participants who undergo rejection will have liver function tests every 1-2 weeks during the first month after the diagnosis, and at least every 3 months thereafter. Participants receiving maintenance IS (Arm B-) will have liver function tests every 3 months.

#### 10.5 Transplant Centre Visits

Transplant Centre Visits will be performed every 6 months in all participants. The following will be collected and recorded:

- Interval history
- Treatment-related diseases history (every 6 months)
- Physical examination and vital signs
- Full blood count Biochemistry panel
- Liver function tests
- Metabolic panel
- HrQOL (SF-36v2 and NIDDK questionnaires every year and at last study visit, EQ-5D questionnaire every 6 months and prior to a for-cause biopsy required during or following IS weaning)
- HLA antibodies (at last study visit)
- Diagnosis of biomarkers test (last study visit)
- Blood draw for mechanistic studies (to be collected every 3 months in patients attending routine liver function tests at the Transplant Centre, if feasible)
- Gut microbiome (stool) (at 18 month from randomisation and at last study visit)
- Adverse events
- Concomitant medications

## 10.6 Telephone Visits

During study participation, and between Transplant Centre visits, telephone visits will be conducted to assess compliance with the study protocol. These will be conducted following the performance of each liver function test assessment, and will include:

- Interval history
- Adverse events
- Concomitant medications.

# 10.7 Visit Windows

- Laboratory evaluations should be completed within ± 5 days of the scheduled dates during the weaning period and the 6 months after complete IS withdrawal; within ± 7 days during months 6-12 after complete IS withdrawal; and within ± 2 weeks thereafter.
- All Transplant Centre Visits throughout the study should be completed within ± 2 weeks of the scheduled time points.

# 10.8 Liver Biopsies

Protocol liver biopsies will be performed:

- 1. At screening (to determine eligibility for study participation and to measure the transcriptional biomarker of tolerance);
- 2. 12 and 24 months after complete IS discontinuation for all recipients in Arms A and B+ who successfully withdraw IS;
- 3. 48 months after enrolment for participants on maintenance IS (Arm B-).

Patients who completely discontinue IS but require IS reinstitution on the basis of the 12-month post-withdrawal liver biopsy findings will still undergo a follow-up biopsy 24 months after IS withdrawal. In addition, "for-cause" biopsies will be performed to evaluate allograft dysfunction.

#### 10.9 Liver biopsy procedure

Consent specific for the procedure will be obtained before each protocol or for cause liver biopsy. Liver biopsies will be performed employing 18-gauge or larger needle using a percutaneous technique. Depending on each participating centre's standard practice, transjugular liver biopsies will also be acceptable. A minimum of 20 mm of core tissue will be obtained. Patients will be informed that the liver biopsy procedure may require 2 passes to obtain the required amoung of tissue.

For all biopsies performed during the subject's study participation, the tissue should be preserved for the following 2 purposes: 1) 15 mm (1.5 cm) will be formalin fixed and paraffin imbedded; 2) the remaining (at least 5 mm) will be placed in RNAlater and sent to King's College Hospital Liver Histopathology Laboratory.

Each site's local Pathology laboratory will keep 1 H&E slide after local reading, and the rest of the slides bearing stained and unstained tissue sections as well as the paraffin block will be sent to King's College Hospital Histopathology Laboratory. Appendix 4 contains a detailed protocol on how to process the formalin-fixed and paraffin embedded sample.

#### 10.10 Assessment of liver biopsies

All liver biopsies performed within the trial will be evaluated both locally and by a central pathologist (blinded to biomarker status). Eligibility criteria, definition of primary endpoint (Table 4), and indication for reinstitution of IS in patients without allograft dysfunction (Table 5) will be determined on the basis of the central pathologist read. In addition, the central read will be used for all study data analyses. Analysis of for-cause biopsies for the purposes of clinical management will be conducted by the local pathologists. The central pathology read of four-cause biopsies will be made available to the sites for consideration at their discretion.

All biopsies read by the central pathology core will be scored employing a pre-defined histopathology review form (Appendix 5). Biopsies will be assessed for adequacy, length, and the total number of portal tracts and central veins. Necro-inflammatory activity and fibrosis will be graded according to the Ishak scale and according to Venturi et al. (26). AR- and CR-related activity will be graded and staged according to Banff criteria.

#### 10.11 Transient elastography assessment (FibroScan®)

All participants will undergo transient elastography assessments using FibroScan at screening and every 12 months (visits M12, M24, M36, M48). Elastography results in isolation should not be employed to modify the management of study participants (e.g. modifying immunosuppressive doses or indicating a for-cause biopsy).

# 11. VISITS AND PROCEDURES SCHEDULE

#### 11.1 Table 2: Transplantation Centre Visits Schedule

Assessment / Visit	Baseline	Screening	М	М	М	М	М	М	М	М	М
	- 7 Wks	- 4 Wks	0	6	12	18	24	30	36	42	48
Informed consent	Х										
Demographics: gender, DOB, ethnicity	Х										
Height and weight	Х										
Medical history (pre & post transplantation)	Х										
Interval history 		Х	Х	Х	Х	Х	Х	Х	Х	Х	Х
Treatment-related diseases history			Х	Х	Х	Х	Х	Х	Х	Х	Х
Physical examination	Х	Х	Х	х	Х	Х	Х	Х	Х	Х	X
Vital signs	Х	Х	Х	х	Х	Х	Х	Х	Х	Х	X
Liver biopsy 		X 									X 
Diagnosis of biomarker test		Х									X
Biochemistry panel	Х	Х	Х	х	Х	Х	Х	Х	Х	Х	X
Hematology (FBC)	Х	Х	Х	х	Х	Х	Х	х	х	Х	Х
Liver function tests 	Х	Х	Х	х	Х	Х	Х	Х	Х	Х	X
Blood/ urine HCG test (females only)	Х										
HLA type of recipient and of donor (if available)	Х										
Autoantibody panel	Х										
IS drug 12-hour trough levels (as appropiate)	Х	Х	Х	Х	Х	Х	Х	Х	Х	Х	Х
Viral serology	Х										
MDRD eGRF	Х										
Inc. / Exc. Criteria	Х	Х	Х								
Metabolic panel			Х	х	Х	Х	Х	х	х	х	X
Blood draw for mechanistic studies 		Х	Х	х	Х	Х	Х	Х	Х	Х	X
Gut microbiome		Х				Х					X
Health Economics Questionnaire				х	Х	Х	Х	Х	Х	Х	X
EQ-5D Questionnaire			Х	х	Х	Х	Х	х	х	х	X
SF-36 and NIDDK Questionnaires			Х		Х		Х		Х		Х
Randomisation			Х								
Adverse Events 	Х	Х	Х	Х	Х	Х	Х	Х	Х	Х	Х
Concomitant Medication 	Х	X	Х	х	Х	Х	Х	х	х	Х	X
Fibroscan		Х			Х		х		Х		X

Information will also be collected during telephone visits (following each liver function test assessment).
 Protocol liver biopsies additional to screening one will be performed at 12 and 24 months post successful IS

weaning or at 48 months post randomization for patients on maitenance IS treatment.

Additional arm-specific schedule of liver function test monitoring is outlined in section 10.4.

Performed every three months for patients undergoing liver function test monitoring at the Transplant Centre.
 Wks weeks prior to randomization

M months from randomization

M0 randomisation visit

3

		~	Period														2			
Assessments	Volume (mL)	Screening	М 0	M 3	M 6	M 9		M 15	M 18		M 24			M 33	M 36			M 45	M 48	Rejection
Frozen PBMC (flow cytometry, epigenetic studies)	50	x	x		x		x		x		x				x				x	x
Whole blood Tempus tubes (gene expression profiling)	6	x	x		x		x		x		x		x		x		x		x	x
Serum (HLA alloantibodies)	5	x	x				x												x	x
Plasma (miRNA/microvesicles)	5	Х	Х	X 	Х	X 	Х	X 	Х	X 	Х	X 	Х	X 	Х	X 	Х	Х	Х	Х
Serum (iron metabolism)	5	Х	Х	X 1	Х	X 	Х	X 1	Х	X 1	Х	X 	Х	X 	Х	X 	Х	Х	Х	Х
Plasma (cytokine assays)	5	Х	Х		Х		Х		Х		Х		Х		Х		Х		Х	Х
Serum (metabolomic profile)	5	Х	Х		Х		Х		Х		Х		Х		Х		Х		Х	Х
Stool sample (gut microbiome)		Х							Х										Х	
Urine sampes (metabolomic profile)			х						х										Х	
Liver biopsy (gene expression) 		X 							X2										X 	Х

